5.4 Dose Modifications

5.4.1 Cabozantinib Dose Levels

Dose Level	Cabozantinib Dosage
0	40 mg daily
-1	20 mg daily

Missed or vomited doses of cabozantinib should be considered missed and not made up.

5.4.2 Nivolumab and Ipilimumab Dose Levels

Missed doses of nivolumab and ipilimumab drugs should not be made up if not administered within the window specified by the protocol. Administration of nivolumab and ipilimumab should remain synchronized for patients on both drugs. No dose levels or schedule changes exist for nivolumab and ipilimumab – the drugs are either administered (together for the combination arm) or held at each given time. If held they may be given at the next specified interval in the protocol.

If all treatment is held for more than 56 days (8 weeks), the patient must be permanently discontinued from study therapy unless study chair approval is obtained for unusual circumstances.

5.4.3 General principles for management of toxicity with combination therapy

The combinations of cabozantinib and immunotherapy are still investigational, and unanticipated or synergistic side effects may be observed. Toxicity from combination therapy may be difficult to attribute to cabozantinib versus nivolumab (with or without ipilimumab). Guidance is provided below in defining attribution by holding cabozantinib, or by empirically starting corticosteroids.

As a general approach, it is suggested that AEs be treated with supportive care when possible at the earliest signs of toxicity. The below management guidelines are provided based on what is known individually about cabozantinib and nivolumab/ipilimumab, with additional guidance in the areas of overlap. They are not mandatory and investigator discretion may be used.

There are many circumstances in which the instructions below dictate permanent discontinuation of therapy. If an investigator feels that it is in the patient's best interest to continue on study therapy, study chair approval may be obtained prior to restarting drug.

Table of relative likelihood of cabozantinib-related and immune-related toxicities.

++ More common

+ Less common

- Infrequent

Toxicity	Cabozantinib-related	Immune-related	Protocol management section
Diarrhea	++	++	5.4.6
Nausea and Vomiting	++	+	5.4.7
Oral mucositis	++	-	5.4.8
Hand-foot syndrome (palmar-plantar erythrodysesthesia syndrome)	++	-	5.4.8
Skin Rash	+	+	5.4.8
Transaminitis (AST/ALT increased)	+	++	5.4.9
Hyperbilirubinemia (bilirubin increased)	-	+	5.4.9
Amylase/lipase increased; pancreatitis	+	-	5.4.9
Pneumonitis	+	++	5.4.10
Hypothyroidism	++	++	5.4.11
Adrenal insufficiency	-	+	5.4.11
Neurologic events	-	+	5.4.12
Renal dysfunction	-	-	5.4.13
Proteinuria	+	-	5.4.13
Fatigue	++	++	5.4.14
Fever	-	-	5.4.15
Infusion reaction	N/A	-	5.4.16
Thrombosis/embolism	+	-	5.4.17
Hypertension	++	-	5.4.18
Cardiomyopathy/myocarditis	-	+	5.4.19
Hemorrhagic events	+	-	5.4.20
Fistula formation/perforation	+	-	5.4.21
Wound healing problems	+	-	5.4.22
Osteonecrosis of the jaw	+	-	5.4.23
Cardiac QTc prolongation	+	-	5.4.24

5.4.4 Cabozantinib-associated adverse events

Most adverse events related to cabozantinib should start to improve within 1-2 weeks of drug hold with supportive management. For patients with possible cabozantinib toxicity of any grade, the investigator has the option to hold cabozantinib to determine whether the toxicity resolves (therefore it is more likely from cabozantinib) or the toxicity persists (therefore it is more likely from immunotherapy). If the toxicity is more likely from cabozantinib, the investigator has the option to continue cabozantinib, or dose reduce one level. If cabozantinib has already been dose reduced and toxicity recurs, it

may be permanently discontinued while the other study drug(s) are continued, if appropriate.

5.4.5 Immune-related adverse events

Immune-related adverse events can happen with any onset in relationship to immune therapy administration, even months after discontinuation of therapy. Corticosteroids are the mainstay of therapy for immune-related adverse events. Most should improve or resolve with an adequate dose of steroids. Prior to starting corticosteroids or hormone replacement for any reason, appropriate endocrine testing including cortisol, ACTH, TSH and reflex T4 to document baseline is strongly recommended.

Please note that in some cases the treatment algorithms recommend steroids if symptoms do not resolve in 7 days. However, this recommendation is not meant to delay steroid treatment at any time it is clinically indicated. Any patient started on corticosteroids initially who is determined to not require steroid treatment for an autoimmune adverse event may resume therapy after an observation period without further symptoms at the discretion of the investigator. Any patients who require additional immune suppressive treatment beyond steroids should go off immune therapy study treatment (but may continue cabozantinib as appropriate).

If AE's are felt to be immune related and drugs are held, nivolumab and ipilimumab should either be given together or both held. Cabozantinib may be either continued, or held, as felt appropriate by the investigator depending on the particular toxicity. The study chair may be contacted for individual circumstances to provide additional guidance.

5.4.6 Diarrhea

Overall management of diarrhea:

Management of diarrhea may be challenging for patients on combination therapy on this protocol, because cabozantinib and immune-related diarrhea have different etiologies and management.

In general, cabozantinib-associated diarrhea tends to be more crampy (not painful) and generally mild in nature. If there is bloody colitis, or abdominal pain, also consider the likelihood of immune-related colitis.

For patients on cabozantinib containing arms, it is suggested they hold for grade 2 and higher diarrhea to monitor for clinical improvement. Antidiarrheals may be used. If the diarrhea is refractory to 1 week or more of drug hold, a trial of steroid therapy may be indicated according to the immune-mediated management algorithm below. Rechallenge may be considered for grade 3 and below diarrhea after resolution to grade 1, but for grade 4 diarrhea study chair approval is required after resolution before rechallenge.

Management of cabozantinib-associated diarrhea:

[figure not shown]
Subjects should be instructed to notify their physician immediately at the first signs of poorly formed or loose stool or an increased

frequency of bowel movements. Guidelines for the evaluation and management of diarrhea are shown in the table below. Administration of antidiarrheal/antimotility agents can be considered for diarrhea as initial management, but are not generally recommended for immune related colitis. Some subjects may require concomitant treatment with more than one antidiarrheal agent. When therapy with antidiarrheal agents does not control the diarrhea to tolerable levels, cabozantinib should be temporarily interrupted or dose reduced. When the diarrhea is controlled, retreatment with cabozantinib may be acceptable per investigator decision. In addition, general supportive measures should be implemented such as continuous oral isotonic hydration, correction of fluid and electrolyte abnormalities, small frequent meals, and stopping lactose-containing products, high-fat meals, and alcohol.

Recurrent or prolonged diarrhea can be associated with anal or perianal skin erosions which increase the risk for anal abscesses, fistulas, or proctitis. Good personal hygiene should be emphasized. Regular examinations of the perianal region should be performed whenever diarrhea has occurred during treatment with cabozantinib. Infections of the perianal region should be treated per local guidelines.

GI Adverse Event Management Algorithm

Rule out non-inflammatory causes. If non-inflammatory cause is identified, treat accordingly and continue I-O therapy. Opiates/narcotics may mask symptoms of perforation. Infliximab should not be used in cases of perforation or sepsis.

Patients on IV steroids may be switched to an equivalent dose of oral corticosteroids (e.g. prednisone) at start of tapering or earlier, once sustained clinical improvement is observed. Lower bioavailability of oral corticosteroids should be taken into account when switching to the equivalent dose of oral corticosteroids.

5.4.7 Nausea and Vomiting

Management of cabozantinib-associated nausea and vomiting:

Antiemetic agents are recommended as clinically appropriate for treatment or prophylaxis of nausea and vomiting, along with supportive care. Dehydration and electrolyte abnormalities may be associated with vomiting and monitoring for and correction of fluid and electrolyte disturbances should be implemented. The dose modification guidance should be followed for non-hematologic events (Section [5.4.25](#)).

The 5-HT3 receptor antagonists are recommended over chronic use of NK-1 receptor antagonists and dexamethasone (NK-1 receptor antagonists can induce or inhibit CYP3A4, and glucocorticoids induce CYP3A4 and thus could lower cabozantinib exposure.)

Immune-related nausea and vomiting

Other GI N-V	Management/Next Dose for Nivolumab+/-Ipilimumab
≤ Grade 1	No change in dose.
Grade 2	Hold pending evaluation for gastritis duodenitis and other immune adverse events or other causes. Resume at same dose level after resolution to ≤ Grade 1.
Grade 3	Hold pending evaluation until ≤ Grade 1. Resume at same dose level. If symptoms do not resolve within 7 days with symptomatic treatment patients should go off protocol therapy
Grade 4	Off protocol therapy
Patients with grade 2 or 3 N-V should be evaluated for upper GI inflammation and other immune related events.	

5.4.8 Stomatitis, Mucositis, and Skin Rash

Management of cabozantinib-associated stomatitis/mucositis:

Preventive measures may include a comprehensive oral examination to identify and treat any potential risk for complications before study treatment is initiated. Appropriate correction of local factors should be instituted as indicated, such as modification of ill-fitting dentures and appropriate care of gingivitis. During treatment with cabozantinib, good oral hygiene and standard local treatments such as non-traumatic and non-irritating cleansing, and oral rinses (eg, with a weak solution of salt and baking soda) should be maintained. Lips should be kept moisturized with lip balm. The use of lipstick, lip-gloss, and Vaseline should be avoided.

Local treatment should be instituted at the earliest onset of symptoms. Obtain bacterial/viral culture if oral infection is suspected and treat infection as clinically indicated.

Management of cabozantinib-associated skin conditions:

Palmar-plantar erythrodysesthesia syndrome (PPES; also known as hand-foot syndrome), skin rash (including blister, erythematous rash, macular rash, skin exfoliation, dermatitis acneiform, and papular rash), pruritus, dry skin, erythema, pigmentary changes, and alopecia have been reported with cabozantinib. All subjects on study should be

advised on prophylactic measures including the use of emollients, removal of calluses, avoidance of exposure of hands and feet to hot water leading to vasodilatation, protection of pressure-sensitive areas of hands and feet, and use of cotton gloves and socks to prevent injury and keep the palms and soles dry.

Early manifestations include tingling, numbness, mild hyperkeratosis, and symmetrical red and swollen areas on the palms and soles. The lateral sides of the fingers or periungual zones may also be affected. Adequate interventions are required to prevent worsening of skin symptoms such as blisters, desquamations, ulcerations, or necrosis of affected areas. Analgesics may be required for pain control.

Treatment guidelines for stomatitis and other general skin reactions should be followed as in Section [5.4.25](#)

Treatment guidelines for hand-foot reactions related to study treatment are presented in the table below.

Rev. Add3

Cabozantinib associated Hand-Foot Reactions

CTCAE Grade	Action To Be Taken
Grade 1	Cabozantinib treatment may be continued at the current dose if PPES is clinically insignificant and tolerable. Otherwise, cabozantinib should be reduced to the next lower dose level. ^a Start urea 20% cream twice daily AND clobetasol 0.05% cream once daily. Reassess at least weekly; if PPES worsens at any time or does not improve after 2 weeks, proceed to the intervention guidelines for Grade 2.
Grade 2	Cabozantinib treatment may be continued if PPES is tolerated. Cabozantinib should be dose reduced or interrupted if PPES is intolerable. Continue urea 20% cream twice daily AND high potency steroid cream (eg, clobetasol 0.05%) once daily and add analgesics (eg, NSAIDs/gamma-aminobutyric acid agonists) for pain control if needed. Reassess at least weekly; if PPES worsens or affects self-care, proceed to the intervention guidelines for Grade 3.
Grade 3	Interrupt cabozantinib treatment until severity decreases to Grade 1 or 0. Continue treatment of skin reaction with high potency steroid cream (eg, clobetasol 0.05%) twice daily AND analgesics. Resume study drug at a reduced dose if PPES recovers to Grade ≤ 1 . Discontinue subject from study treatment if PPES does not improve within 6 weeks.

CTCAE, Common Terminology Criteria for Adverse Events; NSAID, non-steroidal anti-inflammatory drug; PPES, palmar plantar erythrodysesthesia syndrome.

^a Permitted dose levels are defined by individual protocols.

[figure not shown]
GABA, γ -aminobutyric acid; NSAID, nonsteroidal anti-inflammatory drugs; PPE, palmar-plantar erythrodysesthesia

Immune-related skin rash and oral lesions

Skin Rash and Oral Lesions	Management/Next Dose for Nivolumab+/-Ipilimumab
≤ Grade 1	No change in dose *
Grade 2	Hold* until 1≤ Grade resolved. Resume at same dose level.
Grade 3	Hold* until ≤ Grade 1. Resume at same level at investigator discretion
Grade 4	Off protocol therapy

*Patients with purpuric or bullous lesions must be evaluated for vasculitis, Steven-Johnson syndrome, TEN, and autoimmune bullous disease including oral lesions of bullous pemphigus/pemphagoid. Pruritus may occur with or without skin rash and should be treated symptomatically if there is no associated liver or GI toxicity. Note skin rash typically occurs early and may be followed by additional events particularly during steroids tapering.
	

Recommended management: See Skin AE management Algorithm
	

Skin Adverse Event Management Algorithm

Rule out non-inflammatory causes. If non-inflammatory cause, treat accordingly and continue I-O therapy.

Patients on IV steroids may be switched to an equivalent dose of oral corticosteroids (e.g. prednisone) at start of tapering or earlier, once sustained clinical improvement is observed. Lower bioavailability of oral corticosteroids should be taken into account when switching to the equivalent dose of oral corticosteroids.

*Refer to NCI CTCAE v4 for term-specific grading criteria.

Rev. Add3

5.4.9 Hepatobiliary Disorders

Management of cabozantinib-associated hepatobiliary disorders:

The following tables should be used for dose modifications for AST/ALT elevations and/or bilirubin elevations:

Cabozantinib associated Transaminase and/or Bilirubin Elevations

Notes	In general, it is recommended that subjects with elevation of ALT, AST, and/or bilirubin have more frequent laboratory monitoring of these parameters, i.e. 2 or more times per week. If possible, hepatotoxic concomitant medications and alcohol should be discontinued in subjects who develop elevated transaminases.
Transaminase elevation Grade	Intervention
Subjects with AST and ALT less than or equal to the ULN at baseline	
Grade 1	Continue cabozantinib and consider weekly monitoring of liver function tests (LFTs) until stable. Then resume the standard protocol-defined monitoring of LFTs.
Grade 2	Continue cabozantinib with weekly monitoring of LFTs for 6 weeks. If LFTs continue to rise within Grade 2, hold cabozantinib treatment. Then continue with weekly LFTs until resolution to Grade \leq 1. Study treatment may then be resumed at a one-dose-level reduction of cabozantinib
Grade 3	Hold cabozantinib treatment and monitor with twice weekly LFTs until Grade \leq 2. Then continue with weekly LFTs until resolution to Grade \leq 1. Cabozantinib may then be resumed at a one-dose-level reduction.
Grade 4	Discontinue all study treatment permanently. LFTs should be monitored as clinically indicated, at least 2-3 times per week, until resolution to Grade \leq 1. If the subject was unequivocally deriving clinical benefit, the subject may be able to resume treatment at a lower dose of cabozantinib as determined by the investigator and Study Chair but only with Study Chair approval.
Subjects with AST or ALT above the ULN but \leq 3.0 x ULN (i.e., Grade 1) at baseline	
\geq 50% increase of AST or ALT AND both AST and ALT are \leq 5.0 x ULN	Continue cabozantinib treatment with weekly monitoring of LFTs for 8 weeks. If LFTs continue to rise, hold all study treatment. Then continue with weekly LFTs until resolution to Grade \leq 1. Study treatment may then be resumed at a one-dose-level reduction of cabozantinib.
\geq 50% increase of AST or ALT and at least one of AST or ALT is Grade 3 (i.e. AST or ALT $>$ 5.0 but \leq 20.0 x ULN)	Hold all study treatment and monitor with twice weekly LFTs until Grade \leq 2. Then continue with at least weekly LFTs until resolution to Grade \leq 1. Study treatment may then be resumed at a one-dose-level reduction of cabozantinib.

Grade 4	Discontinue all study treatment permanently. LFTs should be monitored as clinically indicated, i.e. 2 times per week or more, until resolution to Grade ≤ 1. If the subject was unequivocally deriving clinical benefit, the subject may be able to resume treatment with cabozantinib at a lower dose as determined by the investigator and Study Chair but only with Study Chair approval.
Bilirubin elevation Grade	
Grade 2 Bilirubin	Continue study treatment. Consider more frequent monitoring of bilirubin, i.e. weekly or more
Grade 2 or greater Bilirubin (and > 2.0 ULN), with Grade 3 or greater transaminase elevation, without evidence of biliary obstruction (i.e. elevation of alkaline phosphatase) or alternative explanation	Permanently discontinue all study treatment due to likely signal of severe liver injury
Grade 3 Bilirubin (> 3.0 ULN), isolated	Hold all study treatment until recovered to Grade ≤ 1 or baseline, INR < 1.5 ULN or baseline, and aminotransferases Grade ≤ 1 or baseline. Cabozantinib may then be resumed at a one-dose-level reduction.
Grade 4 Bilirubin (> 10.0 ULN)	Permanently discontinue cabozantinib

Cabozantinib associated asymptomatic Lipase or Amylase Elevations

NOTES: Amylase and lipase elevations have been observed in clinical studies with cabozantinib. The clinical significance of asymptomatic elevations of enzymes is not known but in general have not been associated with clinically apparent sequelae. It is recommended that subjects with lipase elevation and/or symptoms of pancreatitis have more frequent laboratory monitoring of lipase and/or amylase (2-3 times per week). Subjects with symptomatic pancreatitis should be treated with standard supportive measures.

Asymptomatic Lipase or Amylase Elevations

Grade 1 or Grade 2	Continue at current dose level. More frequent monitoring is recommended
Grade 3	Hold all study treatment Monitor lipase and amylase twice weekly Upon resolution to Grade ≤ 1 or baseline, study treatment may be restarted at the same dose or at a reduced dose provided that this occurs within 4 weeks. If retreatment following Grade 3 lipase or amylase elevation is at the same cabozantinib dose and Grade 3 or Grade 4 elevations recur, then all study treatment must be held again until lipase and amylase levels have resolved to Grade ≤ 1 or baseline and retreatment must be at a reduced dose.
Grade 4	Hold all study treatment Monitor lipase and amylase twice weekly Upon resolution to Grade ≤ 1 or baseline and if resolution occurred within 4 days, cabozantinib may be restarted at the same dose or a reduced dose. If resolution took more than 4 days, the dose must be reduced upon retreatment provided that resolution occurred within 4 weeks. If retreatment following Grade 4 lipase or amylase elevation is at the same cabozantinib dose and Grade 3 or 4 elevations recur, then all study treatment must be held again until lipase and amylase have resolved to Grade ≤ 1 or

	baseline and retreatment must be at a reduced dose.
--	-----------------------------------------------------

Cabozantinib-associated Pancreatitis

Pancreatitis	
Grade 3	Hold cabozantinib treatment. Radiographic evaluation is recommended. Monitor lipase and amylase weekly. Upon resolution to Grade ≤ 1 or baseline, cabozantinib may be restarted at a reduced dose.
Grade 4	Permanently discontinue all study treatment. However, if the subject was unequivocally deriving benefit from therapy, cabozantinib treatment may resume at a reduced dose agreed to by the investigator and Study Chair but only with Study Chair approval.

[figure not shown]
Immune-related hepatobiliary disorders

Liver Function AST, ALT, Bilirubin	Management/Next Dose for Nivolumab+-Ipilimumab
≤ Grade 1	Hold until UNL or baseline. Resume at same dose level.
Grade 2	Hold until UNL or baseline. Resume at same dose level.
Grade 3	Off protocol therapy
Grade 4	Off protocol therapy
Continued treatment of active immune mediated hepatitis may exacerbate ongoing inflammation. Holding drug to evaluate LFT changes and early treatment are recommended.	
LFT changes may occur during steroid tapers from other events and may occur together with other GI events including cholecystitis/pancreatitis.	
Recommended management: see Hepatic AE management algorithm	

Pancreatitis Amylase/Lipase	Management/Next Dose for Nivolumab+-Ipilimumab
≤ Grade 1	May continue at same dose level if asymptomatic; consider liver ultrasound and/or abdominal CT scan if no resolution.
Grade 2	May continue at same dose level if asymptomatic; consider liver ultrasound and/or abdominal CT scan if no resolution.
Grade 3	May continue at same dose level if asymptomatic; consider liver ultrasound and/or abdominal CT scan if no resolution.
Grade 4	Hold drug. Perform liver ultrasound and/or abdominal CT scan to rule out radiographic pancreatitis. Resume at same dose level if asymptomatic and no radiographic clinical concerns. Patients who develop symptomatic pancreatitis or DM should be taken off treatment
Patients may develop symptomatic and radiologic evidence of pancreatitis as well as DM and DKA. Lipase elevation may occur during the period of steroid withdrawal and with other immune mediated events or associated with colitis, hepatitis, and patients who have asymptomatic lipase elevation typically have self-limited course and may be retreated.	
For treatment management of symptomatic pancreatitis please follow the Hepatic Adverse Event Management Algorithm	

Hepatic Adverse Event Management Algorithm

Rule out non-inflammatory causes. If non-inflammatory cause, treat accordingly and continue I-O therapy. Consider imaging for obstruction.

Patients on IV steroids may be switched to an equivalent dose of oral corticosteroids (e.g. prednisone) at start of tapering or earlier, once sustained clinical improvement is observed. Lower bioavailability of oral corticosteroids should be taken into account when switching to the equivalent dose of oral corticosteroids.

*I-O therapy may be delayed rather than discontinued if AST/ALT ≤ 8 x ULN and T.bili ≤ 5 x ULN.

**The recommended starting dose for grade 4 hepatitis is 2 mg/kg/day methylprednisolone IV.

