5.4.25 Guidelines for General Toxicities Commonly Associated with Cabozantinib

As a general approach, it is suggested that all AEs be managed with supportive care when possible at the earliest signs of toxicity. Calcium, magnesium, potassium and phosphorus should be kept above the lower limits of the laboratory normal values. Additional information can be found in the Cabozantinib Investigator's Brochure.

Once reduced, the dose of cabozantinib should not be re-escalated.

General Approach to the Management of Other Cabozantinib-Related Non-Hematologic Adverse Events

Dose Modifications of Cabozantinib for Treatment-Related AEs

CTCAE Grade	Recommended Guidelines for Management ^a
Grade 1 AEs	Add supportive care as indicated. Continue cabozantinib treatment at the current dose level if AE is manageable and tolerable.
Grade 2 AEs which are tolerable and are easily managed Grade 2 AEs which are intolerable and cannot be adequately managed	Continue cabozantinib treatment at the current dose level with supportive care. At the discretion of the investigator, cabozantinib should be dose reduced or interrupted. Note: It is recommended that dose holds be as brief as possible.
Grade 3 AEs (except clinically non-relevant laboratory abnormalities)	Cabozantinib should be interrupted unless the toxicity can be easily managed with a dose reduction and optimal medical care. Note: It is recommended that dose holds be as brief as possible.
Grade 4 AEs (except clinically non-relevant laboratory abnormalities)	Subjects should have cabozantinib interrupted immediately. Discontinue cabozantinib unless the following criteria are met: 
• Subject is deriving clear clinical benefit as determined by the investigator• Toxicity can be managed with a dose reduction following recovery to Grade 1 (or baseline) and optimal medical care
NOTE: A table referencing dose delay and modification criteria for specific medical conditions is provided in Section 5.4.3 . Study treatment dose adjustment is only needed if the toxicity was deemed possibly, probably, or definitely related to cabozantinib treatment.	

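### In 5.4.9 the raised-baseline transaminase row can hold all treatment at a value that already meets its own restart condition, and some Grade 2 values fit no row

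*Combined protocol and SAP*

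**What the plan says.** Eligibility criterion 3.2.14 admits patients with AST and ALT up to 3 x ULN. The cabozantinib transaminase table in 5.4.9 therefore splits by baseline. The header of the second group covers values above ULN and up to "3.0 x ULN (i.e., Grade 1) at baseline".

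That group has three rows:

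- **Row 1** is entered on at least a "50% increase of AST or ALT AND both AST and ALT are" no higher than 5.0 x ULN. The first action is "Continue cabozantinib treatment with weekly monitoring of LFTs for 8 weeks". Next comes "If LFTs continue to rise, hold all study treatment. Then continue with weekly LFTs until resolution to Grade" ≤ 1. Study treatment may then resume with cabozantinib reduced by one level.
- **Row 2** is entered on at least a "50% increase of AST or ALT and at least one of AST or ALT is Grade 3", printed as above 5.0 and up to 20.0 x ULN. All study treatment is held at once.
- **Row 3** is Grade 4, with permanent discontinuation unless the Study Chair approves otherwise.

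For nivolumab with or without ipilimumab, the immune-related liver table in the same section says, both at Grade 1 or below and at Grade 2: "Hold until UNL or baseline. Resume at same dose level".

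Section 5.4.1 gives cabozantinib one lower level, 20 mg against 40 mg. Section 5.4.25 adds: "Once reduced, the dose of cabozantinib should not be re-escalated". Section 5.4.3 says that the management guidance is not mandatory and that toxicity on combination therapy may be hard to attribute to one agent.

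**The concern.** Row 1 is entered on a change relative to the patient's own baseline, but it releases the patient on an absolute grade. The two scales need not agree. A patient can be taken off all study drugs for rising enzymes while still at Grade 1, which is the level at which the row permits restart. The hold then asks for no improvement, and what remains is a one-level cabozantinib reduction that 5.4.25 says should not be reversed. A patient with normal baseline at the same absolute value stays on cabozantinib. At the upper end of the permitted baseline range the same mismatch leaves some Grade 2 values without a row.

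The interest is in patient safety and in consistent dosing across sites. These rows act only in the cabozantinib arms (B, C and T), so uneven application would affect dose intensity there and not in Arm A.

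**Working it through.** **Inputs.** All cut points come from the table. Grade 1 is above ULN to 3.0 x ULN (group header) and Grade 3 is above 5.0 to 20.0 x ULN (row 2), so Grade 2 is above 3.0 to 5.0 x ULN. Let b be the baseline and v the value at the hold, both in multiples of ULN, for the enzyme driving the row. The other enzyme is taken to be no higher than Grade 1.

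**Hold against restart.** Row 1 is entered at 1.5b or more. A hold needs a further rise, so v > 1.5b. Restart is permitted at v ≤ 3.0. Both are true at once when 1.5b < v ≤ 3.0, which requires 1.5b < 3.0, that is b < 2.0.

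**Coverage.** A Grade 2 value below the 50% threshold satisfies 3.0 < v < 1.5b, which requires b > 2.0.

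| b | 1.5b | Held values that already meet restart | Grade 2 values in no row |
|---|---|---|---|
| 1.2 | 1.80 | above 1.80 to 3.0 (width 1.20) | none |
| 1.5 | 2.25 | above 2.25 to 3.0 (width 0.75) | none |
| 1.9 | 2.85 | above 2.85 to 3.0 (width 0.15) | none |
| 2.0 | 3.00 | none | none |
| 2.2 | 3.30 | none | above 3.0, below 3.30 |
| 2.5 | 3.75 | none | above 3.0, below 3.75 |
| 3.0 | 4.50 | none | above 3.0, below 4.50 |

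**Single cases.**

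- b = 1.5, held at 2.5: 2.5/1.5 − 1 = 67% rise, Grade 1, restart already met.
- b = 1.5, held at 3.2: 113% rise, Grade 2, restart not met.
- b = 2.0, held at 3.05: Grade 2, restart not met.
- b = 2.5, value 3.5: 40% rise, Grade 2, no row.
- b = 3.0, value 4.4: 47% rise, Grade 2, no row.

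**Row 2.** Going from 3.0 to 5.0 is already a rise of 5.0/3.0 − 1 = 67%, so every Grade 3 value meets the 50% condition. The hold starts above 5.0 x ULN, so restart is never met at the outset. Row 2 has neither problem.

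**Neighbouring rows.** For normal baseline, the Grade 2 row holds cabozantinib only if the rise continues inside Grade 2, so hold and restart share one scale. The isolated Grade 3 bilirubin row, the asymptomatic lipase/amylase rows and the Grade 3 pancreatitis row all accept return to baseline as an alternative to Grade 1. The raised-baseline transaminase rows do not mention baseline in the restart.

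**Against the immune table.** At b = 1.5 and v = 2.5, row 1 lets study treatment resume, and that includes nivolumab (and ipilimumab in Arm C), because the row held all of it. The immune table keeps those drugs on hold at the same value, since 2.5 is above both ULN and the baseline of 1.5.

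**The case against.** The strongest reply is that a reader might infer that a 50% rise alone stops treatment, so that every patient with baseline up to 2.0 x ULN gets a hold of zero length. The documents do not support that. A 50% rise first leads to continued cabozantinib with weekly tests, and the hold needs a further rise. At exactly 2.0 x ULN that further rise is already Grade 2. Resolution also suggests improvement, and resumption is permitted, not required. This limits the problem to b < 2.0 with v ≤ 3.0, but it does not remove it: within that region the written condition is true when the hold starts.

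On coverage, a reader might infer that the uncovered Grade 2 values have no guidance at all. That is too strong. The notes to the table recommend closer monitoring of any elevation. Section 5.4.4 lets the investigator hold cabozantinib for possible toxicity of any grade. The immune table has a Grade 2 row for nivolumab with or without ipilimumab. The general table in 5.4.25 has Grade 2 entries but is headed for other events. So the gap is in this table and is partly filled elsewhere.

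The two liver tables are also split by presumed cause, so different restart points may be intended. That stands where the cause is clear. But 5.4.3 warns that attribution may be difficult and marks raised transaminases as both cabozantinib-related and immune-related.

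Finally, the guidance is advisory, and 5.4.18 mentions re-escalation after blood pressure control, so the bar in 5.4.25 is not uniform. Both points lower the severity. Neither tells a site how to read row 1.

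**Conclusion.** Wrong as written; minor to moderate. Row 1 can hold all study treatment at a value that already satisfies its restart condition when baseline is below 2.0 x ULN and the held value is at or below 3.0 x ULN. For baselines above 2.0 and up to 3.0 x ULN, Grade 2 values with a rise under 50% fit no row of the table. The point at which nivolumab resumes differs from the immune table.

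This rests on the ULN-based grades printed in the table. Section 5.2 sets CTCAE 5.0 for grading, and its liver definitions are not reproduced. If they grade raised-baseline patients differently, the boundaries would move and the table would need to say which definition governs.

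Two further inferences are not supported. One is a count of affected patients: the documents do not give the share entering above ULN. The any-grade ALT rises in the phase I data of section 1.2 (67% and 44%) do not measure a continuing rise of 50% or more over a raised baseline. The other is a demonstrated loss of liver safety or effect on the PFS comparison: a restart without recovery and an earlier dose reduction pull in opposite directions, and nothing in the documents quantifies either.

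**What to change.** In 5.4.9, reconcile the raised-baseline rows:

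- Put the hold and restart conditions of row 1 on a consistent footing, so that one value cannot satisfy both.
- State what governs Grade 2 values with a rise below 50%, by a row or by a cross-reference.
- Align these rows with the other rows of 5.4.9 that refer to baseline.
- Say how resumption of study treatment under row 1 relates to the immune table when the cause is uncertain.
- State which grade definition applies to a patient whose baseline is raised.

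The thresholds are for the sponsor's medical team; none is proposed here. The cost is rewording a few table entries at the next amendment, with no added visits, tests or patients. The log for Addendum 4 already lists a correction of this kind, to the fatigue table in 5.4.14.
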